9.5.4.2 Reporting of Pregnancy and Exposure to Study Drug Through Breastfeeding

Any pregnancy in which the estimated date of conception is either before the last visit or within 28 days of last study treatment, or any exposure to study drug through breastfeeding during study treatment or within 28 days of last study treatment, must be reported.

If an adverse outcome of a pregnancy is suspected to be related to study drug exposure, this should be reported regardless of the length of time that has passed since the exposure to study treatment.

A congenital anomaly, death during perinatal period, an induced abortion, or a spontaneous abortion are considered to be an SAE and should be reported in the same time frame and in the same format as all other SAEs (see Reporting of SAEs [[Section 9.5.4.1](#)]).

Pregnancies or exposure to study drug through breastfeeding must be reported by fax or email as soon as possible but no later than 1 business day from the date the investigator becomes aware of the pregnancy. The contact information for the reporting of pregnancies and exposure to study drug through breastfeeding is provided in the Investigator Study File. The Pregnancy Report Form must be used for reporting. All pregnancies must be followed to outcome. The outcome of the pregnancy must be reported as soon as possible but no later than 1 business day from the date the investigator becomes aware of the outcome.

A subject who becomes pregnant must be withdrawn from study treatment.

Pregnancies in partners of male study subjects do not need to be reported. (revised per Amendment 04)

9.5.4.3 Reporting of Events Associated with Special Situations

9.5.4.3.1 REPORTING OF ADVERSE EVENTS ASSOCIATED WITH STUDY DRUG OVERDOSE, MISUSE, ABUSE, OR MEDICATION ERROR

AEs associated with study drug overdose, misuse, abuse, and medication error refer to AEs associated with uses of the study drug outside of that specified by the protocol. Overdose, misuse, abuse, and medication error are defined as follows:

Overdose	Accidental or intentional use of the study drug in an amount higher than the protocol-defined dose
Misuse	Intentional and inappropriate use of study drug not in accordance with the protocol
Abuse	Sporadic or persistent intentional excessive use of study drug accompanied by harmful physical or psychological effects

Medication error Any unintentional event that causes or leads to inappropriate study drug use or subject harm while the study drug is in the control of site personnel or the subject.

All AEs associated with overdose, misuse, abuse, or medication error should be captured on the Adverse Event eCRF and also reported using the procedures detailed in Reporting of SAEs (Section 9.5.4.1) even if the AEs do not meet serious criteria. Abuse is always to be captured as an AE. If the AE associated with an overdose, misuse, abuse, or medication error does not meet serious criteria, it must still be reported using the SAE form and in an expedited manner but should be noted as nonserious on the SAE form and the Adverse Event eCRF.

Subjects will be monitored for AEs that may signal drug abuse potential during the Treatment Period and the first 4 weeks of the Follow-up Period. Examples of AEs that may signal drug abuse potential are provided in Appendix 3. A detailed listing of AEs that may signal drug abuse potential is provided in the E2909-G000-301 eCRF Completion Guidelines. (revised per Amendment 04)

9.5.4.3.2 REPORTING OF STUDY-SPECIFIC EVENTS

Study-specific events (ocular herpes, new onset seizures, and symptomatic cerebral vasogenic edema), as detailed in Section 9.5.1.5.2 should always be considered as serious important medical events and be entered on the Adverse Event eCRF and reported using the procedures detailed in Reporting of SAEs (Section 9.5.4.1), even if the study-specific event does not meet other serious criteria.

9.5.4.4 Expedited Reporting

The sponsor must inform investigators (or as regionally required, the head of the medical institution) and regulatory authorities of reportable events, in compliance with applicable regulatory requirements, on an expedited basis (ie, within specific time frames). For this reason, it is imperative that sites provide complete SAE information in the manner described above.

9.5.4.5 Breaking the Blind

In the case of a medical emergency where the appropriate treatment of the subject requires knowledge of the study treatment given, the investigator may break the randomization code for an individual subject. In all such cases, the AE necessitating the emergency blind break will be handled as an SAE in accordance with the procedures indicated above. Any broken code will be clearly justified and documented. The medical monitor must be notified immediately of the blind break.

9.5.4.6 Regulatory Reporting of AEs

AEs will be reported by the sponsor or a third party acting on behalf of the sponsor to regulatory authorities in compliance with local and regional law and established guidance. The format of these reports will be dictated by the local and regional requirements.

All studies that are conducted within any European country will comply with European Good Clinical Practice Directive 2005/28/EC and Clinical Trial Directive 2001/20/EC. All SUSARs will be reported, as required, to the competent authorities of all involved European member states.

9.5.5 Completion/Discontinuation of Subjects

A subject may elect to withdraw from the study at any time for any reason. All subjects who discontinue study drug early for any reason will undergo an ED Visit within 7 days of their last dose of study drug (see [Section 9.1.2.2](#)). In addition, Follow-Up Visits will be scheduled 4 and 12 weeks after the last dose of study drug (Visit 14 and Visit 15, respectively) (see [Section 9.1.2.2](#)). These Follow-up Visits will be conducted to monitor efficacy and safety parameters after early withdrawal from the study or discontinuation of study drug. See [Table 5](#) for full details of the assessments to be performed at these visits.

All subjects who discontinue study drug before reaching 12 months of treatment will also be asked to return to the clinic for a 12 month clinical assessment and then again at 24 months. Subjects who discontinued treatment between 12 and 24 months of treatment will be asked to return to the clinic for a 24-month clinical assessment. Subjects who discontinue early from study drug are considered “on study” as long as they continue to return for their clinical assessments at 12 and 24 months as outlined above, at which efficacy and quality of life will be assessed along with concomitant medications and AEs. However, subjects who discontinue study drug early are not considered to have ‘completed’ the study as a final Subject Disposition. A subject removed from the study for any reason may not be replaced.

The investigator will promptly explain to the subject involved that the study will be discontinued for that subject and provide appropriate medical treatment and other necessary measures for the subject. A subject who has ceased to return for visits will be followed up by mail, phone, or other means to gather information such as the reason for failure to return, the status of treatment compliance, the presence or absence of AEs, and clinical courses of signs and symptoms.

The primary reasons for early withdrawal from the study are: AE, lost to follow-up, subject choice, withdrawal of consent, pregnancy, study terminated by sponsor, and other. The secondary reasons for early withdrawal from the study are: AE, subject choice, and other.

The primary reasons for early discontinuation from the study drug are: AE, subject choice, pregnancy, inadequate therapeutic effect, and other. The secondary reasons for early discontinuation from the study drug are: AE, subject choice, inadequate therapeutic effect, and other.

9.5.6 Abuse or Diversion of Study Drug

AEs associated with abuse or diversion will be appropriately reported as AEs and monitored per [Section 9.5.1.5.1](#). Abuse is always to be captured as an AE.

During the study, the investigator should be aware of the possibility of abuse or diversion of study drugs and should report any concern about mishandling, abuse, loss, theft, or diversion of study drugs by completing the Abuse or Diversion of Study Drug eCRF.

9.5.7 Confirmation of Medical Care by Another Physician

The investigator will instruct subjects to inform site personnel when they are planning to receive medical care by another physician. At each visit, the investigator will ask the subject whether he or she has received medical care by another physician since the last visit or is planning to do so in the future. When the subject is going to receive medical care by another physician, the investigator, with the consent of the subject, will inform the other physician that the subject is participating in the clinical study.

9.6 Data Quality Assurance

This study will be organized, performed, and reported in compliance with the protocol, standard operating procedures, working practice documents, and applicable regulations and guidelines. Site audits will be made periodically by the sponsor's or the CRO's qualified compliance auditing team, which is an independent function from the study team responsible for conduct of the study.

9.6.1 Data Collection

Data required by the protocol will be collected on the eCRFs and entered into a validated data management system that is compliant with all regulatory requirements. As defined by ICH guidelines, the CRF is a printed, optical, or electronic document designed to record all of the protocol-required information to be reported to the sponsor on each study subject.

Data collection on the eCRF must follow the instructions described in the CRF Completion Guidelines. The investigator has ultimate responsibility for the collection and reporting of all clinical data entered on the eCRF. The investigator or designee as identified on Form FDA 1572 (where applicable) must sign the completed eCRF to attest to its accuracy, authenticity, and completeness.

Completed, original eCRFs are the sole property of Eisai and should not be made available in any form to third parties without written permission from Eisai, except for authorized representatives of Eisai or appropriate regulatory authorities.

9.6.2 Clinical Data Management

All software applications used in the collection of data will be properly validated following standard computer system validation that is compliant with all regulatory requirements. All data, both eCRF and external data (eg, laboratory data), will be entered into a clinical system.

Electronic source (eSource) methodology may be used for some of the clinical efficacy and HRQoL assessments performed in this study.

9.7 Statistical Methods

All statistical analyses will be performed by the sponsor or designee. Statistical analyses will be performed using SAS software or other validated statistical software as required.

All statistical tests will be based on the 5% (2-sided) level of significance, unless specified.

For statistical methods specific to the Extension Phase, refer to [Appendix 5 in Section 12](#).

9.7.1 Statistical and Analytical Plans

All statistical analyses will be performed by the Sponsor or designee after the study is completed and the database is locked and released for unblinding. All statistical analyses will be performed based on the pooled data from 2 studies (E2609-G000-301 and E2609-G000-302). The analyses will also be performed within each study to confirm the trend of the efficacy and biomarker endpoints unless specified. (revised per Amendment 06)

9.7.1.1 Study Endpoints

9.7.1.1.1 PRIMARY ENDPOINT

The primary endpoint of the study is:

- Change from baseline in the CDR-SB at 24 months in the combined studies (revised per Amendment 06)

9.7.1.1.2 SECONDARY ENDPOINTS

The key secondary endpoints of the study are as follows (revised per Amendment 06):

- Change from baseline in ADCOMS at 24 months in the combined studies
- Change from baseline in amyloid PET SUVR at 24 months for brain amyloid levels in the combined studies
- Change from baseline in amyloid PET SUVR at 24 months for brain amyloid levels in the individual studies

The other secondary endpoints of the study are as follows (revised per Amendment 06):

- Change from baseline in the CDR-SB at 24 months for subjects enriched by baseline PET SUVR, eg, between 1.2 and 1.6, in the combined studies
- Change from baseline in the ADCOMS at 24 months for subjects enriched by baseline PET SUVR, eg, between 1.2 and 1.6, in the combined studies
- The rate of change over time (mean slope) based on CDR-SB score over 24 months in the combined studies
- Time to worsening of CDR scores by 24 months (eg, the worsening of global CDR score is defined as an increase from baseline by at least 0.5 points on the global CDR scale on 2 consecutive scheduled visits at which global CDR is undertaken) in the combined studies
- Time to conversion to dementia by 24 months for subjects who were not clinically staged as dementia at Baseline based on clinical diagnosis in the combined studies (revised per Amendment 01)
- Change from baseline in CDR-SB at 27 months (ie, 24 months of treatment plus 3 months posttreatment follow-up) in the combined studies (revised per Amendment 01)
- Change from baseline in ADAS-cog14, MMSE, and FAQ at 24 months in the combined studies
- Change from baseline in ADAS-cog14 Word List (immediate recall and delayed recall) at 24 months in the combined studies (revised per Amendment 01)

9.7.1.1.3 BIOMARKER ENDPOINTS

The biomarker endpoints of the study are:

- Change from baseline in tau PET signal at 24 months (revised per Amendment 05)
- Change from baseline in CSF biomarkers t-tau and p-tau at 24 months
- Change from baseline in CSF amyloid biomarkers A β (1-42), and A β (1-x) at 24 months (revised per Amendment 04)
- Change from baseline in plasma amyloid biomarker (eg, A β (1-x)) at all assessments (revised per Amendment 06)
- Change from baseline in potential plasma and CSF biomarkers of AD (eg, NFL, VILIP1, YKL-40, and Ng) (revised per Amendment 06)
- Change from baseline in total hippocampal volume at 24 months using vMRI
- Change from baseline in the preservation of connectivity on fMRI at 24 months (revised per Amendment 01)

9.7.1.1.4 EXPLORATORY ENDPOINTS

The exploratory endpoints of the study are:

- Time to change of concomitant AD treatment (ie, dose increase and/or initiation of treatment with AChEI or memantine after randomization) by 24 months
- The proportion of subjects at 24 months who received dose increases and/or initiation of treatment with AChEI or memantine after randomization
- The rate of change over time (mean slope) based on NPI-10 item score over 24 months
- Change from baseline in NPI-10 item at 24 months
- Change from baseline in EQ-5D (subject self-reported, study partner self-reported, and subject measured by proxy) and QOL-AD (subject and study partner) at 24 months
- Change from baseline in Zarit's Burden Interview at 24 months

9.7.1.2 Definitions of Analysis Sets

- The Randomized Set is the group of subjects who are randomized to study drug.
- The Safety Analysis Set is the group of subjects who receive at least 1 dose of study drug and have at least 1 postdose safety assessment.
- The Full Analysis Set (FAS) is the group of randomized subjects who receive at least 1 dose of study drug and have baseline and at least 1 postdose primary efficacy measurement.
- The Per Protocol Analysis Set (PPS) is the subset of subjects in the FAS who sufficiently comply with the protocol. The PP Analysis Set will be used to conduct a sensitivity analysis of the primary efficacy endpoint. Details of the evaluability criteria will be determined before database lock and treatment unblinding, and will be specified in the statistical analysis plan.
- The PK Analysis Set is the group of subjects with at least 1 quantifiable elenbecestat plasma concentration with a documented dosing history.
- The PD Analysis Set is the group of subjects who have sufficient PD data to derive at least 1 PD parameter.

9.7.1.3 Subject Disposition

The number of subjects screened, the number (percent) of subjects who failed screening, and the reasons for screen failure will be summarized, based on data reported on the Screening Disposition eCRF. The distribution of the number of randomized subjects enrolled by each site will be summarized for each randomized treatment group. The primary reasons for screen failures (did not meet inclusion or met exclusion criteria, AE, lost to follow-up, withdrawal of consent, and other) will be presented.

Study Completion: the number (percent) of randomized and treated subjects who completed the study and who discontinued from the study will be summarized according to the primary reason for discontinuation and secondary reason(s) for discontinuation, based on data reported on the Subject Disposition (Study Phase) CRF. The number (percent) will be presented by treatment group and total for subjects; randomized, not treated, treated, who completed the study, and discontinued from the study. The primary reasons for early withdrawal from the study are: AE, lost to follow-up, subject choice, withdrawal of consent, pregnancy, study terminated by sponsor, and other. The secondary reasons for early withdrawal from the study are: AE, subject choice, and other.

Completion of Study Treatment: the number (percent) of randomized and treated subjects who completed study drug and who discontinued from study drug will be summarized according to the primary reason for discontinuation and also according to secondary reason(s) for discontinuation, based on data reported on both the Subject Disposition (Study Phase) eCRF and ED from Study Drug eCRF. The number (percent) will be presented by treatment group and total for subjects; randomized, not treated, treated, who completed study drug, and discontinued from study drug. The primary reasons for early discontinuation from the study drug are: AE, subject choice, pregnancy, inadequate therapeutic effect, and other. The secondary reasons for early discontinuation from the study drug are: AE, subject choice, inadequate therapeutic effect, and other.

9.7.1.4 Demographic and Other Baseline Characteristics

Demographic and other baseline characteristics for the Safety Analysis Set and FAS will be summarized for each treatment group using descriptive statistics. Continuous demographic and baseline variables include age, CDR scores, ADAS-cog14, MMSE and FAQ; categorical variables include sex, age group (equal or less than 65 years, age greater than 65 years), race, ethnicity, region, *ApoE4* genotype, prior treatment with AChEIs or memantine (no or yes), and clinical subpopulation (MCI due to AD or the early stages of mild AD). (revised per Amendment 01)

9.7.1.5 Prior and Concomitant Therapy

All investigator terms for medications recorded in the eCRF will be coded to an 11-digit code using the World Health Organization Drug Dictionary (WHO DD) (Mar 2014). The number (percentage) of subjects who took prior and concomitant medications will be summarized on the Safety Analysis Set by treatment group, Anatomical Therapeutic Chemical class, and WHO DD preferred term (PT). Prior medications will be defined as medications that stopped before the first dose of study drug. Concomitant medications will be defined as medications that (1) started before the first dose of study drug and were continuing at the time of the first dose of study drug, or (2) started on or after the date of the first dose of study drug up to the date of the last dose. All medications will be presented in subject data listings.

Medications taken within the 12-week Follow-up Period will also be recorded.

9.7.1.6 Efficacy Analyses

The FAS will be used as the primary population for all efficacy analyses, while the PPS will be used as the supportive population.

9.7.1.6.1 PRIMARY EFFICACY ANALYSIS

The primary analysis will be based on an intent to treat philosophy without regard to adherence to treatment. The primary analysis of the change from baseline in CDR-SB at 24 months will be performed to compare elenbecestat 50 mg per day versus placebo using a linear mixed effects model for repeated measures (MMRM) on the FAS. The MMRM model will include fixed effects of treatment group, visit, treatment group by visit interaction, baseline CDR-SB, baseline CDR-SB by visit interaction, and randomization stratification variables (ie, region [7 levels], clinical dementia [yes, no], and concurrent AD medication use at randomization [Visit 2] [yes, no]). *ApoE4* status may be included in the model if appropriate. (revised per Amendments 01, 02, and 06) An unstructured covariance matrix will be employed to model the covariance of within subject effect; if MMRM fails to converge then a covariance structure with fewer parameters from the following list will be employed according to the prespecified order in the list until the MMRM converges. The list of covariance structure will include Heterogeneous Toeplitz, Toeplitz, Heterogeneous Compound Symmetry, and Compound Symmetry. This primary analysis will include all observed post baseline data of the change from baseline in CDR-SB without imputation of missing values. The treatment effect for elenbecestat versus placebo will be compared at 24 months based on MMRM model. The LS means and difference in LS means between elenbecestat treatment group and placebo, and corresponding 95% CI will be presented.

The null hypothesis is that there is no difference in the mean change from baseline in CDR-SB at 24 months between elenbecestat 50 mg per day and placebo. The corresponding alternative hypothesis is that there is a difference in the mean change from baseline in CDR-SB at 24 months between elenbecestat 50 mg per day and placebo.

The primary analysis will be repeated to minimize the impact of change in concomitant AD medications where efficacy data after initiation of new AD medications and increase of current AD medications will be censored.

The following sensitivity analysis will be conducted to evaluate the impact of missing data: the primary endpoint will be analyzed using ANCOVA after multiple imputation. The ANCOVA model will include baseline CDR-SB as a covariate, with treatment group and randomization stratification variables as factors. *ApoE4* status may be included in the model if appropriate. Additional sensitivity analyses will be performed to assess the robustness of the missing at randomization assumption in the primary MMRM model. Subgroup analysis (eg, stratification factors and *ApoE4* status) and additional sensitivity analysis for the primary endpoint will be performed as appropriate. (revised per Amendments 01 and 06)

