9.7.2 Determination of Sample Size

The sample size for this study is estimated for comparison of elenbecestat versus placebo with respect to a pooled analysis of studies E2609-G000-301 and E2609-G000-302 for the change from baseline in CDR-SB at 24 months. Based on the available data from the placebo group in Study BAN2401-G000-201 (a recently completed study with a comparable subject population), the mean and the standard deviation of the change from baseline in CDR-SB at 24 months in the placebo group are assumed to be 1.46 and 2.05, respectively, instead of 1.75 and 2.05, which are originally assumed by the available data from ADNI (of amyloid positive, MMSE equal or greater than 24, late MCI [global CDR=0.5, CDR memory box \geq 0.5]). Therefore, assuming a 25% reduction in the mean change from baseline CDR-SB at 24 months for elenbecestat compared to placebo with common standard deviation of 2.05 and 30% dropout rate, a total sample size of 1900 subjects, 950 subjects in each treatment group, will be required to detect the treatment difference between elenbecestat and placebo using a 2-sample t test with 90% power at a significance level of 2 sided alpha =0.05.

The pooled data from 2 studies (E2609-G000-301 and E2609-G000-302) will comprise the total sample size of approximately 1900 subjects. At least 850 subjects will be randomized in each study. (revised per Amendment 06)

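### The pooled primary MMRM has no study term and does not cross dementia stage with visit; adding both is a nearly free gain in precision, not a repair of an invalid test

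*Protocol*

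**What the plan says.** Protocol Sections 8.1 and 9.7.1.1.1 place the primary objective and endpoint in the combined studies. Section 9.7.1 states: "All statistical analyses will be performed based on the pooled data from 2 studies (E2609-G000-301 and E2609-G000-302". Section 9.7.2 adds: "At least 850 subjects will be randomized in each study".

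Section 9.7.1.6.1 then writes the primary model out term by term. The sentence opens "The MMRM model will include fixed effects of treatment group, visit, treatment group by visit interaction, baseline CDR-SB"; its terms in full are "fixed effects of treatment group, visit, treatment group by visit interaction, baseline CDR-SB, baseline CDR-SB by visit interaction, and randomization stratification variables". The last item is spelled out as "randomization stratification variables (ie, region [7 levels], clinical dementia [yes, no], and concurrent AD medication use at randomization [Visit 2] [yes, no". The one optional addition is ApoE4, which "status may be included in the model if appropriate". On covariance: "An unstructured covariance matrix will be employed to model the covariance of within subject effect".

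The omission carries over. In Section 9.7.1.6.2 the same model serves ADCOMS, amyloid PET, the PET-enriched subgroup and the other continuous endpoints. The slope model crosses only baseline and treatment with time. The Cox models adjust for the stratification factors. The ANCOVA after multiple imputation (Section 9.7.1.6.1) uses baseline, treatment and the stratification factors. None names study.

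Section 9.7.1 also provides a supportive look by study: "The analyses will also be performed within each study to confirm the trend of the efficacy and biomarker endpoints unless specified".

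**The concern.** Study is a design factor of the pool, with its own minimum enrolment, yet the pooled model does not use it. A single-study model has no need of such a term; a pooled one does. If the two studies decline at different rates, the difference stays in the residual.

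The second omission is of the same kind. The outcome is a change score that builds up over 24 months, so groups declining at different speeds drift apart with time. The plan recognises this for baseline CDR-SB, which it crosses with visit. The stratification variables get one constant shift over all visits, which cannot describe a gap that is small at Month 3 and largest at Month 24, the visit that is tested.

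At stake are some precision at Month 24 and, if dropout is uneven in a particular way, a small bias.

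**Working it through.** **1. The plan's own figure.** Inputs from Section 9.7.2: placebo mean 1.46, SD 2.05, 25% reduction, 30% dropout, 90% power, two-sided 0.05.

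- Difference: 0.25 × 1.46 = 0.365.
- Per arm: 2 × (1.96 + 1.2816)² × (2.05/0.365)² = 663.
- With dropout: 663/0.70 gives 948 per arm, 1896 in all, against 1900 stated. It reproduces.
- With 950 × 0.70 = 665 completers per arm, power is 0.901.

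This is a plain two-sample t test, so the sample size does not depend on the missing terms.

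**2. Study alone, closed form.** With half the subjects in each study, a difference d in 24-month change contributes 0.25 × d² to a variance of 2.05² = 4.2025. The values of d are assumptions; 0.73 is half the assumed placebo mean.

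| d | Share of variance | SD after removal | Power, 665 per arm (0.9009 unadjusted) |
|---|---|---|---|
| 0.2 | 0.24% | 2.048 | 0.9016 |
| 0.4 | 0.95% | 2.040 | 0.9036 |
| 0.73 | 3.17% | 2.017 | 0.9098 |

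**3. Both omissions in an MMRM.** Assumed set-up: eight CDR visits, unstructured covariance, linear decline, 1900 subjects split evenly between studies and arms, 25% with dementia, 30% dropout spread over the earlier visits, the same within-group spread throughout. Study and stage differences refer to 24-month change. Baseline CDR-SB, region and AD medication are not in this calculation. Power for an effect of 0.365:

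| Study / stage difference | Plan's terms | + study | + study×visit | + stage×visit | Both interactions |
|---|---|---|---|---|---|
| 0 / 0 | 0.9407 | 0.9407 | 0.9407 | 0.9407 | 0.9407 |
| 0.4 / 0.5 | 0.9373 | 0.9379 | 0.9392 | 0.9389 | 0.9407 |
| 0.4 / 1.0 | 0.9327 | 0.9332 | 0.9346 | 0.9389 | 0.9407 |
| 0.73 / 1.5 | 0.9200 | 0.9220 | 0.9266 | 0.9346 | 0.9407 |

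The estimate is −0.365 in every cell: no bias with or without the terms. The power lost is 0.9407 − 0.9373 = 0.3 points, 0.9407 − 0.9327 = 0.8 points and 0.9407 − 0.9200 = 2.1 points. All values exceed 0.90 because the MMRM uses the partial data of dropouts: its standard error is 0.1037, against 2.05 × √(2/665) = 0.1124 for completers only. A study main effect alone does little; study by visit does more.

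**4. Uneven dropout, no drug effect.** Negative values favour active.

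- *By stage:* dropout 25% on placebo, 30% in active MCI, 50% in active dementia (30% overall). For differences 0.4/1.0 and 0.73/1.5 the plan's terms give a bias of −0.0266 and −0.0390, with type I error 0.0573 and 0.0650. With stage by visit added: 0 and 0.0500.
- *By study:* dropout 20% (25% in dementia), plus 20 points in the active arm of one study (26.2% overall). The bias is −0.0131 and −0.0231, with type I error 0.0518 and 0.0554. A study main effect alone leaves −0.0142 and −0.0252. Study by visit leaves −0.0006 and −0.0009, with type I error 0.0500.

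Against the assumed effect, 0.0131/0.365 = 3.6% and 0.0390/0.365 = 10.7%.

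**The case against.** **Main effects for strata are a standard, valid choice, and baseline by visit already carries severity over time.** This largely stands. Under Section 9.3.1 every subject enters with MMSE of at least 24 and global CDR 0.5, so the two stages lie close together. The calculation gives no credit to baseline by visit, so the real gain from stage by visit is likely to be smaller than tabulated.

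**The assumed differences have no source.** This stands. Taking the 25% dementia share, which Section 9.1 sets as a cap, a stage difference of 1.5 means 1.46 + 0.75 × 1.5 = 2.585 points of decline against 1.46 − 0.25 × 1.5 = 1.085, a ratio of 2.4. A study difference of 0.73 is large for two studies that Section 9.2.1 describes with one design. The upper ends are extremes.

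**A pooling factor can be left to the SAP.** This stands only in part. The explicit list closes the stratification variables, and a SAP could add a term. But the protocol does not leave the model open: it states it term by term, with ApoE4 as the only option.

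**Separate randomisation by study is inferred.** This stands. Section 9.4.3 describes the scheme for this study, and the protocol of Study 302 is not at hand. The minimum number to be randomised in each study makes the inference reasonable, and study remains a factor of the pool either way.

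**The within-study analyses cover it.** This does not stand. They are there to confirm the trend and do not adjust the pooled test.

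**Conclusion.** Both omissions are in the current text, and correcting them is an improvement at almost no cost. The primary test is valid as written and 1900 subjects remain adequate. Under the assumed differences the loss runs from about 0.1 point of power (a study difference of 0.2 alone) to about 2 points (0.73 and 1.5 together), and power stays above 90% in all the scenarios.

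Three stronger readings are tempting and not supported:

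- *That pooling without a study term biases the estimate.* With about 1:1 allocation in each study (Section 9.1 gives the ratio for this one) and equal dropout, the bias is zero.
- *That the plan has an inflated type I error.* The range 0.052 to 0.065 needs a 20-point dropout excess in the active arm confined to one stage or study, together with the larger assumed differences. Nothing in the protocol predicts that pattern, and the reverse pattern would work against active.
- *That the Month 24 variance left by a constant stage effect can be bounded by averaging the visits equally.* The unstructured covariance does not weight visits equally, so no such bound follows.

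**What to change.** In Section 9.7.1.6.1, add study and study by visit to the pooled primary MMRM, and dementia stage by visit. Then:

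- add study and study by visit to the pooled continuous-endpoint models that reuse it;
- add study and study by time to the pooled slope model;
- add study to the ANCOVA after multiple imputation;
- stratify the pooled Cox models by study.

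Do not add study to the within-study analyses, including the key secondary amyloid PET analysis by study: it is constant there and cannot be estimated. Do not require region by visit in the smaller, optional PET substudy. Report the consistency of the treatment effect across studies descriptively, not as a condition for the pooled test.

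The cost is protocol and SAP wording, settled before unblinding. With eight visits the primary model gains 1 + 7 = 8 parameters for study and 7 for stage by visit, 15 in all for about 1900 subjects. Crossing every stratification variable with visit would take (6 + 1 + 1) × 7 = 56, which is not needed.
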